1 INTRODUCTION

The 2018 International Contact Lens Prescribing report¹ describes 32% of soft lenses are prescribed on a daily disposable (DD) basis worldwide (27% in US), compared with 13% and 51% on a one-to-two week and monthly replacement schedule, respectively (30% and 41% in US). There has been an upward trend in prescribing daily disposables for several years.²

Until recently, DD lenses were mainly available in a hydrogel material. However, in line with the increasing market share of DD lens modality, more and more new silicone hydrogel (SiHy) DD lenses are becoming available. One of these new SiHy DD lenses are Precision1 lenses that has been recently introduced by Alcon.

This study will evaluate the performance of Alcon's Precision1 compared to CooperVision's clariti 1 day. All participants will habitually wear soft contact lenses, but they do not have to habitually wear daily disposable lenses. Participants from BOXER (EX-MKTG-107, phases 1 or 2) and MIKI (EX-MKTG-114) studies are not allowed to take part in this study. All lenses used in this study are spherical, silicone hydrogel daily disposables lenses that are approved by Health Canada.

2 OBJECTIVES

The objective of the study is to evaluate and compare the performance of Alcon's Precision1 lens (P1) to clariti 1 day (C1D), when worn on a daily disposable modality over a period of approximately one week each. C1D is considered the study test lens. P1 will be the control lens.

The primary outcome variables of this study are:

- Subjective ratings for 'Lens handling for lens insertion' (0 - 10 integer scale) for TEST lens compared to CONTROL, collected at the 1-week visit reflecting on a 'typical day' experience during the study;
- Subjective ratings for 'Lens handling for lens removal' (0 - 10 integer scale) for TEST lens compared to CONTROL, collected at the 1-week visit reflecting on a 'typical day' experience.

The secondary outcome variables are:

- Centration (optimal, slight decentration, moderate decentration but not encroaching limbus, excessive & occasionally encroaching limbus), collected at dispense & 1-week visit;
- Post-blink movement in primary gaze, mm, collected at dispense & 1-week visit;

Participants will be randomized to wear either the test or the control lens first. All lenses will be worn in a daily disposable lens wear modality for one week (-1/+3 days). The study involve up to 5 scheduled visits. The study design is shown in Figure 1.

[figure not shown]

Figure 1: Study Design, visits 1 & 2 may be on a single day, also visits 3 & 4 may be on a single day.

Visit 1: Includes screening, baseline assessments, fitting of both study lenses.

Visit 2: Dispense lens pair #1 (either test or control lens, randomized).

Visit 3: 1-week follow-up assessment of lens pair #1

Visit 4: Dispense of lens pair #2 (either test or control lens)

Visit 5: 1-week follow-up assessment of lens pair #2 and study exit.

- Participants will complete the following in-office subjective ratings on paper using a numeric rating scale (0 – 10) at visits 3 and 5 for each lens type:
- Lens handling;
- [REDACTED]
- [REDACTED]
- [REDACTED]
- [REDACTED]

[REDACTED]

[REDACTED]

[REDACTED]

[REDACTED]

- [REDACTED]
- [REDACTED]
- [REDACTED]
- [REDACTED]

- [REDACTED]
- [REDACTED]
- [REDACTED]
- [REDACTED]
- [REDACTED]

4.1.3 RANDOMIZATION

A randomization schedule will be generated using a web-based program: (for example www.randomization.com) by CORE's Data management team, and provided to the research assistants for the study. The schedule will determine the order of lens wear for participants in the study. Study investigators will remain masked to the randomization schedule until the study is completed and the database has been locked.

4.1.4 MASKING

Participants will be masked to the lens assignment. Lenses dispensed to participants may be either over-labelled or have part of the label obscured, however the safety information shall be clearly visible. Investigators will be masked as much as possible however it may not be possible to fully mask the investigators, because identifying lens markings may be visible during the biomicroscopy examination.

5 STUDY POPULATION

5.1.1 SAMPLE SIZE CALCULATION

[REDACTED]

[REDACTED]

[REDACTED]

[REDACTED]

A total sample size of 47 is recommended to detect a mean difference between lens handling for insertion of 0.8 units on the 0 to 10 scale using a standard deviation of 1.9 with 80% power and alpha 0.05 in a two-tailed t-test. Therefore, the sample size needed for BASSET will be aimed at 28 to complete (i.e. total of 47 minus the 19 completed participants from the BOXER phase 1 pilot study). Therefore, it is recommended that at least 31 subjects are dispensed in the BASSET study, with a target of 28 to complete.

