5.1.2 NUMBER OF PARTICIPANTS

Participants will be screened using CORE records and advertising approved by the UW Office of Research Ethics. Approximately 31 participants will be dispensed with study products in the study, with a target of 28 completing the study.

A documented informed consent process will be conducted with all participants prior to their enrolment in the study and prior to any data collection or measurements.

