5.1.3 INCLUSION AND EXCLUSION CRITERIA

A person is eligible for inclusion in the study if he/she:

1. Is at least 17 years of age and has full legal capacity to volunteer;
2. Has read and signed an information consent letter;
3. Is willing and able to follow instructions and maintain the appointment schedule;
4. Habitually wears soft contact lenses in daily wear, for minimum of 6-months;
5. Is correctable to a visual acuity of 20/40 or better (in each eye) with the study lenses;
6. Has an astigmatism of ≤ 1.00 D in subjective refraction;
7. Can be fit with study contact lenses with a power between -0.50 and -10.00 DS;
8. Demonstrates an acceptable fit with the study lenses;
9. Habitually wears single vision soft contact lenses for at least 8 hours per day, 5 days a week, and is willing to wear contact lenses for at least 12 hours a day in the study.

A person may be excluded from the study if he/she:

1. Is participating in any concurrent clinical or research study;
2. Has any known active* ocular disease and/or infection;
3. Has a systemic condition that in the opinion of the investigator may affect a study outcome variable;
4. Is using any systemic or topical medications that in the opinion of the investigator may affect a study outcome variable;
5. Has known sensitivity to the diagnostic pharmaceuticals to be used in the study;
6. Is pregnant, lactating or planning a pregnancy at the time of enrolment because the associated hormonal changes cause changes in the tear layer which impact contact lens comfort. Verbal confirmation at the screening visit is sufficient;
7. Is aphakic;
8. Has undergone refractive error surgery;

9. Is an employee of the Centre for Ocular Research & Education;
10. Has participated in the BOXER (i.e. EX-MKTG-107, phases 1 or 2) or MIKI (EX-MKTG-114) Study, or has any history of wearing one of the study contact lenses;
11. Has participated in any clinical trials within a week prior to the study.

* For the purposes of this study, active ocular disease is defined as infection or inflammation, which requires therapeutic treatment. Mild (i.e. not considered clinically relevant) lid abnormalities (blepharitis, meibomian gland dysfunction, papillae), corneal and conjunctival staining and dry eye are not considered active ocular disease. Neovascularization and corneal scars are the result of previous hypoxia, infection or inflammation and are therefore not active.

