12 STATISTICAL ANALYSIS AND DATA MANAGEMENT

12.1 STATISTICAL ANALYSIS

Primary comparisons will be between study lenses, however there are some variables collected over time with the same lens and this time comparison will be analysed (e.g. 'at-home ratings on Days 1, 3 and 5).

All data will be analyzed by CORE at the University of Waterloo. Unmasked data analysis will be conducted using Statistica, SPSS, or other appropriate software. Descriptive statistics will be provided on information regarding baseline variables (age, gender, refractive error distribution, etc.). Table 6 lists the main outcome variables and anticipated statistical procedures. All data will be tested for normality of distribution using Shapiro-Wilk tests.

Results for logMAR will be reported and analysed for binocular acuity and in some cases data of right eye only will be analysed and reported (e.g. lens fit variables, biomicroscopy).

Data from 'at-home' ratings Day 5 will be analysed to determine the mean 'cumulative comfort score', as described by Keir et al.³

A binomial test will be used to analyze the results for the count data of subjective preferences.

Table 6: Statistical analysis to be conducted

Variable	Analysis	Statistical test
Subjective ratings	Descriptive and other statistics	Mean, Median*, Standard Deviation, Minimum, Maximum, Frequency count
	Effect of treatment on outcome variable within subjects (comparison between study days) Effect of time on ratings (comparison over time)	Friedman Wilcoxon matched pairs test
Visual acuity; NITBUT; lens centration and movement; limbal, bulbar and tarsal redness; corneal and conjunctival staining	Descriptive statistics	Mean, Median*, Standard Deviation, Minimum, Maximum, Count
	Effect of treatment on outcome variable within subjects (comparison between study days)	RMANOVA Paired t-test

* For non-parametric data only

The critical alpha level for statistical significance will be set at 0.05, with no adjustments for multiple comparisons.

All participants who were evaluated will be included in the analysis, unless their removal is agreed by the sponsor due to protocol deviations and/or adverse events. In the event of missing data, individual data points will not be extrapolated from the collected data.

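### The 80% power in Section 5.1.1 belongs to 47 participants, 19 of them from BOXER, but readable Section 12.1 names no combined dataset; BASSET alone has about 57% power

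*Combined protocol and SAP*

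**What the plan says.** Section 5.1.1 gives a total of 47 to detect a mean difference of 0.8 units in insertion handling on the 0 to 10 scale, "using a standard deviation of 1.9 with 80% power and alpha 0.05 in a two-tailed t-test". It then states that the BASSET sample is "aimed at 28 to complete (i.e. total of 47 minus the 19 completed participants from the BOXER phase 1 pilot study". Section 5.1.2 carries this forward: "Approximately 31 participants will be dispensed with study products in the study, with a target of 28 completing the study".

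The BOXER participants cannot be enrolled in BASSET. Section 1 says "Participants from BOXER (EX-MKTG-107, phases 1 or 2) and MIKI (EX-MKTG-114) studies are not allowed to take part in this study", and exclusion criterion 10 in Section 5.1.3 applies to anyone who "Has participated in the BOXER (i.e. EX-MKTG-107, phases 1 or 2) or MIKI (EX-MKTG-114) Study".

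Section 12.1 defines the analysis population in one sentence: "All participants who were evaluated will be included in the analysis", apart from removals agreed by the sponsor. Table 6 in that section assigns Friedman and Wilcoxon tests to the subjective ratings. The section shows no redaction marks. It mentions no BOXER data, combined dataset or study term, and it does not say that BASSET is analysed alone.

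Four blocks of Section 5.1.1 ahead of the calculation are redacted, and the readable text passes from Section 2 to Section 4.1.3.

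**The concern.** Subtracting 19 from 47 makes sense only if the 19 BOXER results enter the test that has 80% power. Because those people are excluded from BASSET, their data must come in from outside, and the analysis section is where a reader would look for that dataset, its model and its status. The readable Section 12.1 does not supply them. Its population sentence reads most naturally as referring to BASSET participants.

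Insertion handling is one of the two primary outcomes and the only one used for the sample size. If the primary test uses BASSET alone, the 80% does not apply to it, and a non-significant result could be taken as evidence of similar handling when the study had a substantial chance of missing the planned difference. If the primary test uses both studies, the reader needs to know that, how the studies are combined, and what BASSET shows by itself.

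**Working it through.** **Inputs, all from Section 5.1.1:** difference 0.8; SD 1.9; two-sided alpha 0.05; 80% power; total 47; BOXER credit 19; BASSET 28 completers from 31 dispensed. The section does not say whether 1.9 is the SD of paired differences or of ratings on one lens. Each participant wears both lenses (Section 2), so the comparison is within person.

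**Step 1: reproduce 47.** For a paired t-test, power comes from the noncentral t distribution with n − 1 degrees of freedom and noncentrality (0.8/1.9) × √n = 0.421 × √n.

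- n = 46: 0.421 × √46 = 2.86, power 79.8%.
- n = 47: 0.421 × √47 = 2.89, power 80.7%.

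So 47 is the smallest n that reaches 80% when 1.9 is the SD of paired differences. A two-group formula with SD 1.9 gives 89 per group, which does not fit.

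**Step 2: BASSET alone, same inputs.**

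- n = 28: 0.421 × √28 = 2.23, power 57.5%. A true 0.8-unit difference is missed about 43% of the time.
- n = 31 (nobody drops out): 0.421 × √31 = 2.34, power 62.1%.
- Difference detectable with 80% power: 1.04 units at n = 28, 0.99 at n = 31, 0.79 at n = 47.
- Expected 95% CI half-width, t × 1.9/√n: 2.05 × 1.9/√28 = 0.74 at n = 28; 2.01 × 1.9/√47 = 0.56 at n = 47.

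**Step 3: the test in Table 6.** With a Wilcoxon matched-pairs test on simulated normal differences (20,000 samples), power is about 55% at n = 28, 60% at n = 31 and 79% at n = 47. The choice of test changes little.

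**Step 4: the other reading of 1.9.** If 1.9 were the SD of ratings on one lens, the SD of differences would be 1.9 × √(2(1 − ρ)), where ρ is the within-person correlation. The documents give no ρ. For assumed values of 0.3, 0.5 and 0.7, the n for 80% power is 64, 47 and 29, and power at 28 is 44%, 57% and 79%. Of these, only ρ = 0.5 returns 47, and there the two readings coincide: 1.9 × √(2 × 0.5) = 1.9.

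**Step 5: what pooling does to the error rates.** Suppose pooling was fixed whatever BOXER showed, and the BOXER differences have the same mean and SD as those in BASSET. The test on 19 + 28 = 47 is then an ordinary test on 47 differences. Averaged over possible BOXER results, its power is about 81% and its false-positive rate 5%. Rates conditional on the BOXER result actually seen are different. For illustration only, take an assumed BOXER mean difference of 0, 0.4 or 0.8 with SD 1.9. The pooled test then succeeds 34%, 65% or 87% of the time at a true 0.8, and gives false positives 1%, 4% or 15% of the time at a true 0. The readable text gives no BOXER results, so these figures show a direction and carry no weight in the conclusion.

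**The case against.** The strongest objection is the redaction. The blocked text in Section 5.1.1 sits immediately before the calculation, where BOXER and any pooling rule would naturally be described. Because protocol and SAP are one document, a rule stated there would be part of the plan. That stands, and it limits the point: a reader might infer that the plan never provides for pooling, or that it contradicts itself, and the documents do not support either. What remains is that Section 12.1 does not carry through, or refer back to, the 47-participant dataset on which the sample size rests.

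A reader might also infer that using 19 completed results by itself invalidates the 80% and 5%. It does not. If pooling was decided regardless of the BOXER result, both hold on average (step 5). They fail only conditionally on the observed BOXER result, or if the decision to pool was driven by it. The readable text does not say when or why the decision was made.

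A third inference would be that "Unmasked data analysis will be conducted using Statistica, SPSS, or other appropriate software" lets the dataset be chosen after outcomes are seen. Section 12.1 does not say that outcomes are seen before lock, and Section 4.1.3 states: "Study investigators will remain masked to the randomization schedule until the study is completed and the database has been locked". The word unmasked adds little here.

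Finally, the 57% is conditional on how 1.9 is read. That is a fair caveat, though the reading used is the one that reproduces 47.

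**Conclusion.** The concern holds as a mismatch between Sections 5.1.1 and 12.1. The stated 80% describes a combined set of 47. BASSET's 28 completers alone give about 57% power for 0.8 units, and 80% only for about 1.04 units. These figures rest on 1.9 being the SD of paired differences and on a paired t-test; the Wilcoxon test gives nearly the same. That pooling was intended is an inference from the subtraction, since no readable passage states it. Confidence is medium because of the redactions. This should be fixed, but it does not undermine the design.

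**What to change.** In Section 5.1.1:

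- State that 1.9 is the SD of paired differences, if it is.
- State that the 80% applies only to the combined 47, and give the BASSET-alone figures: about 57% power for 0.8 units, or 80% power for about 1.04 units, with 28 completers.
- State whether pooling was decided before the BOXER results were known. If it was, the nominal 80% and 5% hold on average. If it was not, say that the error rates depend on the BOXER result.

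In Section 12.1:

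- Name the primary dataset before database lock: BASSET alone, or BOXER phase 1 plus BASSET.
- If it is combined, include study as a factor and report the BASSET-alone estimate and 95% CI beside the combined result.

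The cost is a few sentences and a less favourable stated power for BASSET alone. No extra participants are needed.

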5.1.2 NUMBER OF PARTICIPANTS

Participants will be screened using CORE records and advertising approved by the UW Office of Research Ethics. Approximately 31 participants will be dispensed with study products in the study, with a target of 28 completing the study.

A documented informed consent process will be conducted with all participants prior to their enrolment in the study and prior to any data collection or measurements.

5.1.3 INCLUSION AND EXCLUSION CRITERIA

A person is eligible for inclusion in the study if he/she:

1. Is at least 17 years of age and has full legal capacity to volunteer;
2. Has read and signed an information consent letter;
3. Is willing and able to follow instructions and maintain the appointment schedule;
4. Habitually wears soft contact lenses in daily wear, for minimum of 6-months;
5. Is correctable to a visual acuity of 20/40 or better (in each eye) with the study lenses;
6. Has an astigmatism of ≤ 1.00 D in subjective refraction;
7. Can be fit with study contact lenses with a power between -0.50 and -10.00 DS;
8. Demonstrates an acceptable fit with the study lenses;
9. Habitually wears single vision soft contact lenses for at least 8 hours per day, 5 days a week, and is willing to wear contact lenses for at least 12 hours a day in the study.

A person may be excluded from the study if he/she:

1. Is participating in any concurrent clinical or research study;
2. Has any known active* ocular disease and/or infection;
3. Has a systemic condition that in the opinion of the investigator may affect a study outcome variable;
4. Is using any systemic or topical medications that in the opinion of the investigator may affect a study outcome variable;
5. Has known sensitivity to the diagnostic pharmaceuticals to be used in the study;
6. Is pregnant, lactating or planning a pregnancy at the time of enrolment because the associated hormonal changes cause changes in the tear layer which impact contact lens comfort. Verbal confirmation at the screening visit is sufficient;
7. Is aphakic;
8. Has undergone refractive error surgery;

9. Is an employee of the Centre for Ocular Research & Education;
10. Has participated in the BOXER (i.e. EX-MKTG-107, phases 1 or 2) or MIKI (EX-MKTG-114) Study, or has any history of wearing one of the study contact lenses;
11. Has participated in any clinical trials within a week prior to the study.

* For the purposes of this study, active ocular disease is defined as infection or inflammation, which requires therapeutic treatment. Mild (i.e. not considered clinically relevant) lid abnormalities (blepharitis, meibomian gland dysfunction, papillae), corneal and conjunctival staining and dry eye are not considered active ocular disease. Neovascularization and corneal scars are the result of previous hypoxia, infection or inflammation and are therefore not active.

5.1.4 REPEATED SCREENINGS

In some circumstances, a repeated screening may need to be scheduled. The maximum total number of screenings permitted will be 3 ie. 2 re-screens. Examples of reasons include, but are not limited to:

1. Incomplete information available at time of screening to determine eligibility (e.g. current lens brands worn, history from current eye care practitioner etc.);
2. Study procedures unable to be completed in time scheduled for visit;
3. Study products not available at the time of the screening visit;
4. The short term use of medications (e.g. antibiotics, antihistamines etc.);
5. Reassessment of baseline ocular conditions (e.g. corneal and/or conjunctival staining, scars etc.).

5.2 STUDY MATERIALS

5.2.1 LENSES

All study lenses are approved by Health Canada. They will be worn bilaterally, and on a daily disposable basis, therefore no lens care solution is required.

Table 1: Details of contact lenses to be used in the study

	Clariti 1-Day – Test (CooperVision, Inc.)	Percision1 – Control (Alcon)
Material	somofilcon A	verofilcon a
HC licence #	81009	101910
Dk/t (barrer/cm)	86	100

Water content	56%	51%
Sphere power (D)	-0.50 to -6.00 (0.25 steps) -6.50 to -10.00 (0.50 steps)	-0.50 to -6.00 (0.25 steps) -6.50 to -10.00 (0.50 steps)
Base curve (mm)	8.6	8.3
Diameter	14.1	14.2
Replacement schedule	Daily disposable	Daily disposable

5.2.2 REWETTING DROPS

Participants who habitually use rewetting drops will be asked to refrain during the study, unless necessary for continued lens wear. Participants will keep track of rewetting drop usage, and this will be recorded at each visit. Rewetting drops may be used in the event of any clinical observation and/or adverse event noted during the study.

5.2.3 ORDERING CONSUMABLES

All study lenses (tests and control) will be provided by CooperVision or sourced from local commercial channels.

5.2.4 CONTACT LENS DISPENSING

Lenses will be provided to the participant after being transferred, complete with blister pack solution, to a contact lens cup; this will maintain participant masking and aid investigator masking. The use of saline for rinsing the contact lens prior to insertion is permitted if necessary. Saline will not be dispensed during the study.

5.2.5 CONTACT LENS DISPOSAL

Participants will be instructed to dispose of the worn lenses daily, and return any unworn lenses in their packaging at their next study visit. All contact lenses worn to each 1-week follow up visit will be collected and stored at -80C. These collected lenses will be shipped to CooperVision at the end of the study. The tear film deposits left on these lenses will be evaluated and analysed for composition and quantity, no genetic assessments will be conducted.

Additionally, worn lenses associated with adverse events shall be retained at CORE and returned to CooperVision if requested to do so. Typical analysis in these cases relates to inspection for damage and/ or bacterial contamination. No genetic assessments will be conducted.

Upon completion of the study, all non-dispensed and the returned unworn lenses will be destroyed, unless otherwise directed by the study Sponsor.

